Mild Pain or Discomfort	
Tenderness/minor ache at and/or around dressing application areaDecreased sleep or sleep qualityParesthesia (numbness, tingling, prickling, creeping sensation)
Other	
Risks to privacyLoss of data confidentiality

Potential Risks of a Blood Draw

- Discomfort
- Fainting
- Dizziness
- Bruising at the puncture site (hematoma)
- Nerve injury
- Arterial puncture or laceration

Protection Against Risks

Protected health information (PHI) of subjects in clinical investigations are kept as confidential as possible in accordance with the Health Insurance Portability and Accountability Act of 1996 (HIPAA). However, confidentiality cannot be assured. The table below lists the entities granted access to protected health information (PHI).

Entity	Reason for Access
Sponsor's Clinical Representative (Monitor)	Assess data for accuracy and completeness
Institutional Review Board (IRB)	Ensure protection of research subjects
Regulatory Authorities (e.g. Food and Drug Administration)	Audit clinical trial for Subject protection and data integrity
Investigator/Site Staff	Collection and assessment of data for accuracy and completeness

Alternatives to Participation:

Subjects are not required to participate in this research study. As an alternative to study participation, subjects will receive wound care treatment per physician discretion.

2. Trial Objectives

The primary objective of this trial is to compare the clinical outcomes between cryopreserved and lyopreserved Stravix adjunct to NPWT in the treatment of diabetes-related lower extremity complex wounds.

3. Selection and Withdrawal of Subjects

Inclusion Criteria:

- Diagnosis of a diabetes mellitus
- Men/women ≥ 21 years old
- Post-operative foot or ankle wounds sized $>4\text{cm}^2$ that have presented for <1 year
- ABI ≥ 0.5 or toe pressures >30 mmHg
- Wounds indicated for treatment with NPWT

Exclusion Criteria:

- Active Charcot arthropy
- Unable to use NPWT
- Untreated bone or soft tissue infection
- Is pregnant or plans to become pregnant
- Is nursing or actively lactating
- Developmental disability/significant psychological disorder that in the opinion of the investigator could impair the subject's ability to provide informed consent, participate in the study protocol or record study measures, including untreated schizophrenia, bipolar disorder and psychiatric hospitalization within the last 2 years.

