Primary Endpoint: To compare the incidence of complete wound closure of lyopreserved vs cryopreserved Stravix treated groups at 12 weeks post initial application.

Secondary Endpoints: To evaluate the outcomes noted below between lyopreserved and cryopreserved Stravix.

1. Time to 100% granulation of deep structures (bone, tendon, etc)
2. Duration of NPWT
3. Time to surgical grafting to cover the wound.
4. Time to complete wound closure (complete epithelization with no drainage)
5. Level of infection
6. Quality of Life – SF36, EQ-5D and PROMIS®

Sample Size

For this study, 40 patients from UT Southwestern and Parkland hospitals will complete the study (no cap on screening/enrollment).

Duration of Subject Participation

- Screening: Within 7 days of therapy start
- Treatment period: Up to 12 weeks from therapy start
- Total duration of subject participation: Up to 13 weeks

Screening and Enrollment

Patients who present to the investigator's institution (through clinic admission, direct transfer from another facility, or through the emergency room) may be recruited to participate in the study. No direct marketing for subject recruitment will be done.

Patients approached for study participation will be at least 21 years of age at the time of consent, will undergo wound assessment, and meet all eligibility requirements. Those meeting eligibility criteria for the study will have the study explained to them by the Investigator. An Informed Consent Form will be provided to sign according to Section 11 prior to undergoing any study procedures. Patients will be encouraged to ask questions of the investigators. It will be made clear to the patient that not participating in the study will in no way influence the treatment plan or the relationship with the physician.

There is no cap on the number of subjects that can be screened/enrolled. Additional subjects will continue to be recruited as needed to reach the minimum number of 20 treated per protocol, per arm (40 in total).

Wound Selection

Subjects with only one wound will be included in the study. Subjects with multiple wounds will have each wound measured for volume. The wound with the largest volume meeting all eligibility requirements will be chosen for inclusion in the study as the primary wound. The etiology of the chosen wound, its classification, and if it is a new or recurring, will be documented. All other wounds will be documented as secondary wounds and will be followed throughout the study.

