Randomization

Randomization will be performed using www.randomizer.org. Subjects who meet all inclusion and no exclusion criteria will be randomized in a 1:1 ratio to be treated with NPWT and either lyopreserved Stravix or cryopreserved Stravix. Study staff will use the randomization number labels contained in the envelope. The number will become the subject ID. The research staff will note treatment assignment number on the CRF. ^[17] _[SEP]

Visit Schedule

Study procedures for each phase of study are outlined below. In a later section, details on each study procedure are described, including equipment designation.

Screening

1. Explain purpose and nature of the study and obtain signature on the informed consent document.
2. Screen the subject against protocol inclusion and exclusion criteria, including all pertinent tests

(ex. ABIs), including pregnancy test

3. Complete SF-36, EuroQol 5 dimensions (EQ-5D) and PROMIS®
4. Perform neuropathy assessment
5. Randomize subject if all inclusion and exclusion criteria are met.

Baseline (-within 7 days -after screening)

1. Obtain general medical history and demographic information and social history
2. Complete a physical examination, body weight, height, BMI and vital signs, including measurement of resting heart rate, respiratory rate, and blood pressure while seated.
3. Select target study ulcer
4. Obtain complete history pertinent to DFU disease including duration of the target ulcer, previous and current treatment. Document ulcer classification.
5. Perform debridement and obtain tissue collection (up to 4 tissues and 1 bone if applicable).
6. Collect blood sample at baseline visit (approximately 10mL at each collection) for Ribonucleic Acid (RNA) gene expression.
7. Perform standardized photography and measurement of the primary study wound and, if applicable, secondary study wounds (eKare or available camera with ruler if eKare is not available) pre-debridement. Assess the post-debridement ulcer area (cm^2), perimeter (cm), and greatest depth (cm) using the inSight device (eKare, Fairfax, VA). These values are the baseline measurements for calculating wound closure rate at the two-week run-in visit.
8. Perform hyperspectral imaging of dorsal and plantar aspects of the foot.
9. Collect all relevant concomitant medication (antibiotics, antifungals and other anti-infective therapies)
10. Collect all relevant clinical lab values

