- *Wound History and Evaluation:* We will use the University of Texas Ulcer Classification to document ulcer severity. Our group developed and validated this classification system. This classification system is a 4 x 4 matrix that includes the depth of the ulcer or the ulcer Grade: (1.) pre-ulcerative site, (2.) full thickness, (3.) extends to tendon or capsule, (4.) extends to bone and the Stage of the ulcer that identifies if there is infection and/or PAD: (A.) No PAD or infection, (B.) infection, (C.) PAD (D.) infection and PAD.
- *Wound Measurements and Debridement:* Debridement will be performed per physician discretion using a scalpel or bone curette to remove all surrounding callus, wound debris, necrotic tissue, fibrin, eschar and non-viable tissue to create a bleeding wound bed. Debridement may also take place in a surgical setting in which case tissue samples will be collected. Tissue and bone samples – the doctor will take 4 small samples of tissue from the subject's wound after debridement

(removal of dead or unhealthy tissue) and 1 sample of bone (if applicable) and these tissue samples will be kept and tested for the amount and type of bacteria that are present (qPCR analysis/laboratory analysis). We will objectively measure ulcer debridement and changes in wound size using changes in wound volume and area from wound measurements with the inSight digital 3D measurement device (eKare, Fairfax, VA). Digital photos will be taken after debridement. We will take post-debridement measurements of wound volume and area. Gardner et al reported that volume measurements with a digital image evaluation system was reliable.

- *Safety Measures:* Each of the following measures will be rated on the following 5-point Likert scale, as well as a descriptive evaluation being recorded, as applicable, for the study wound: 1) absence or 2) presence of the following:
 - Erythema
 - Discharge/drainage
 - Malodor
 - Tissue necrosis

Vascular Assessment

We will assess perfusion with three approaches; Arterial dopplers (bedside may be done for screening if formal ABIs have not yet been performed/resulted), and Hyperspectral Imaging. Hyperspectral imaging (HyperMed, Nashville, TN or Kent Imaging, Calgary, AB, Canada) will be used to evaluate the peri-wound tissue surrounding the ulcer and the angiosomes on the dorsum and plantar aspect of the foot.

Neurological Assessment

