Semmes-Weinstein monofilament evaluation will be performed. We will assess light touch and pressure sensation at five sites on the study foot using a 10-gram monofilaments. We will perform Vibration Perception Threshold VPT; a device that uses vibration to test how well your feet can detect gentle pressure.

Infection Evaluation

This system first divides wounds by whether they are clinically infected on the basis of the presence of purulent secretions or local or systemic signs of inflammation or infection. Infected wounds are further divided into those that are considered to be mild, moderate, or severe, on the basis of the size (especially of any cellulitis) and depth (or level of tissue involved) of the infection and presence of systemic manifestations of infection or metabolic instability [4]. Additionally, the subjects will have the following monitored: temperature, heart rate, respirations and WBC.

Description	International Working Group Infection Severity
no infection: no pus no inflammation	1
2 or more signs of infection (pus, pain, warmth, swelling. cellulitis < 2cm infection limited to the skin or subcutaneous tissue	2

No systemic signs of infection	
2 or more signs of infection (pus, pain, warmth, induration. cellulitis > 2 cm lymphangitis, abscess infection extends to deep fascia, tendon muscle No systemic signs of infection	3
same as 3 with systemic toxicity meets SIRS criteria fever >38C, tachycardia >90, respiration >12, leukocytosis >12,000	4
osteomyelitis	5

Patient Reported Outcomes

The Medical Outcomes Study (MOS) 36-item Short Form (SF-36) is one of the most commonly utilized instruments in assessing diabetic foot disease and provides information on overall physical and mental quality of life. The SF-36 provides a physical component summary (PCS) score as well as a mental component summary (MCS) score, which are derived from eight different sub-scales. The PCS and MCS are standardized so that a score of 50 represents the normative score for the general population, and a higher score is indicative of better HRQOL (20). Excellent correlation has been found between PCS and MCS scores calculated from the SF-36 in patients with diabetic foot disease [5].

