We will summarize study variables as means and standard deviations (SD) for continuous variables and proportions or percentages for categorical variables. Continuous variables will be presented as median, mean \pm standard deviation and dichotomous variables presented as percent. We will use Analysis of Variance (ANOVA) to test for differences in continuous variables. For categorical variables, we will use chi square to compare the proportion of outcomes in each treatment arm with an alpha of 0.05, and we will use Kaplan Meier analysis to compare closure rates of the treatment groups. p-values were reported using the step-up Bonferroni method of Hochberg. We will use an adjusted two-sided analysis with an alpha of 0.05. In the intent to treat analysis, we will use the last observation carried forward to define the clinical outcomes for patients that were lost to follow up.

Tissue samples will be extracted and used for molecular biology analyses. These may include, gene and protein expression of the wound tissue, histological analyses of tissue morphology and pathology, and analyses of bacterial genes to determine levels of infection. All sample analyses will be performed in a de-identified manner and tissue samples WILL NOT be used for genetic sequencing that can be used to deduce the subject's identity.

Sample Size Justification

This is a pilot exploratory study so no sample size justification will be provided.

8. Data Management

Standardized CRFs will be used. Investigators are responsible for the accurate completion and timely submission of the data collected during the trial. All data from the trial will be entered from the CRFs into a central database. Incoming data will be frequently reviewed to identify inconsistent or missing data and any adverse events. Any data issues are to be promptly addressed with the investigator by the Sponsor. Quality assurance procedures will be established to ensure that complete, accurate and timely data are submitted, that protocol requirements are followed and that complications, adverse events and adverse device effects are correctly reported and investigated, as appropriate. Investigators are to maintain all source documents as required by the protocol, including laboratory results, supporting medical records, and signed Informed Consent Forms. The source documents will be used during the regular monitoring visits to verify information from the database against data contained on the completed CRFs.

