For all adverse events, the investigator must pursue and obtain information adequate both to determine the outcome of the adverse event and to assess whether it meets the criteria for classification as a serious adverse event requiring immediate notification to the Osiris Therapeutics contact. For all adverse events, sufficient information should be obtained by the investigator to determine the causality of the adverse event. The investigator is required to assess causality. For adverse events with a causal relationship to the device, follow-up by the investigator is required until the event or its sequelae resolve or stabilize at a level acceptable to the investigator, and the Osiris Therapeutics contact concurs with that assessment.

Protocol Specific AE Definition/Collection: For the purposes of this study, only AEs that are directly related to the study product, diabetes (including labs & kidney function) or wound healing (including infections related to the wound) will be collected and reported as these events may effect outcomes and analysis of data. AEs not related to the aforementioned product or diagnoses are not relevant to the subject outcomes of this research or data analysis (such as nausea, emesis, pain, constipation, diarrhea, mood disorders, respiratory diagnoses, etc). AEs that do not fall under this protocol specific definition will be assessed and treated as per standard of care. SAEs will be collected as per the usual SAE guidelines (see section on reporting SAEs). In addition, planned procedures related to the study wound for a subject during the same hospitalization (as these subjects will be recruited while in the hospital because they have an infection in their foot wound/ulcer) for incision/debridement/amputation will be considered part of their continuation of SOC and not adverse events unless a complication, new infection or new wound occurs.

Adverse Event Reporting

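### Infection status at entry is recorded but not used when the arms are compared on level of infection, and the infection grade is assigned to no visit

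*Combined protocol and SAP*

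**What the plan says.** **Who enters.** Section 14 (Protocol Specific AE Definition/Collection) describes the subjects in passing, "as these subjects will be recruited while in the hospital because they have an infection in their foot wound/ulcer". The exclusion list in Section 3 names "Untreated bone or soft tissue infection", so a treated infection does not bar entry. It is not required either. Section 4 (Screening and Enrollment) gives the routes of recruitment as "through clinic admission, direct transfer from another facility, or through the emergency room" and does not mention infection.

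**The endpoint.** Secondary endpoint 5 reads "Level of infection". It has no scale, visit or reference to baseline. Section 4 (Infection Evaluation) gives a 1 to 5 grade in which "Infected wounds are further divided into those that are considered to be mild, moderate, or severe", with osteomyelitis as grade 5. The grade is not among the baseline steps and has no row in the Schedule of Events. Section 7 also speaks of bacterial gene analysis as a way to determine levels of infection.

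**What is recorded at baseline.** Step 4 of the baseline visit says "Document ulcer classification". Section 4 (Wound History and Assessment) describes that classification as including "the Stage of the ulcer that identifies if there is infection and/or PAD"; stages B and D denote infection. Anti-infective drugs and laboratory values (the list includes white cell count, CRP and ESR) are also taken. Tissue for bacterial load is a baseline step, but a schedule footnote limits it to surgical debridement.

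**The analysis.** Section 7 states "For categorical variables, we will use chi square to compare the proportion of outcomes" and uses ANOVA for continuous variables. It names no covariate, change from baseline or infection stratum. Its one use of the word adjusted follows the sentence on the Hochberg method. Section 4 (Randomization) states a 1:1 ratio and no stratification.

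**The concern.** If a sizeable share of subjects start with an infection under treatment, the level of infection at a later visit reflects two things: how infected the wound was at entry, and what happened after the product was placed. A comparison that ignores the first treats it as noise. With 20 subjects per arm that noise can be large, and any chance difference at entry carries into the result uncorrected.

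Entry status also matters elsewhere. In Section 14 a new infection turns a planned in-hospital procedure into an adverse event, which can feed the primary safety endpoint (index-wound adverse events). Section 3 ends participation on certain changes relative to previous measures, infection among them. Section 4 schedules a blood sample for subjects who develop and then recover from an infection. None of these says how an infection persisting from entry is told apart from one that arises later.

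**Working it through.** **1. The plan's own figure.** 2 arms × 20 = 40, as stated. Section 7 calls the study an exploratory pilot and gives no power, effect size or infection rate, so nothing further can be reproduced. Every rate and correlation below is an assumption.

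**2. Collected against used.** The ulcer stage is documented at baseline step 4 and Stravix is placed at step 11, so an infected/not infected flag (B or D v A or C) exists before treatment. No analysis in Section 7 uses it.

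**3. Chance imbalance at entry.** Let X and Y be the numbers infected at entry in two arms of 20, each binomial(20, p). A difference of 4 subjects is 4/20 = 20 points; 6 subjects is 30 points. P(|X − Y| ≥ k) is the sum of b(x; 20, p) × b(y; 20, p) over all pairs with |x − y| ≥ k.

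| p | at least 20 points | at least 30 points |
|---|---|---|
| 30% | 22.6% | 5.6% |
| 50% | 26.8% | 8.1% |
| 70% | 22.6% | 5.6% |

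**4. What an imbalance does.** If the risk of infection at the analysed visit is q1 for subjects infected at entry and q0 for the others, an imbalance of 20 points moves the arm difference by 0.20 × (q1 − q0). For q1 − q0 of 20, 40 or 60 points, that is 4, 8 or 12 points with no product effect at all.

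**5. Error rate.** Over all randomisations the unadjusted chi-square test keeps its level: exact enumeration at 20 per arm gives 3.9% to 5.3% for event rates of 10%, 30%, 50% and 70%. Among simulated trials with an entry imbalance of at least 20 points, however, the false-positive rate of an unadjusted comparison of grades was 6.8%, 9.1% and 11.3% for baseline correlations of 0.4, 0.6 and 0.7. After baseline adjustment it was 4.9%, 4.7% and 6.2%.

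**6. Power.** For a continuous score and a difference of 0.8 SD, approximate power is Φ(0.8 / (√(1 − ρ²) × √(2/20)) − 1.96), where ρ is the baseline correlation.

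- Unadjusted: 0.8/0.316 = 2.53; 2.53 − 1.96 = 0.57; power 72%.
- ρ = 0.3: 2.53/0.954 − 1.96 = 0.69; 76%.
- ρ = 0.5: 2.53/0.866 − 1.96 = 0.96; 83%.
- ρ = 0.7: 2.53/0.714 − 1.96 = 1.58; 94%.

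Simulation of a four-level grade with the same shift, 3,000 trials per setting, compared a rank test with rank ANCOVA. Power went from about 63% to 66% (correlation 0.4), 61% to 73% (0.6) and 64% to 81% (0.7). Adjusting only for an infected/not infected flag, as the ulcer stage would allow, raised power from about 61–64% to 66–75%, with error near 5%.

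**7. Loss under the plan's own test.** Suppose infection arising after placement is 40% v 10%, and a fraction c of each arm counts as infected because of entry status. The compared proportions are c + (1 − c) × 0.40 and c + (1 − c) × 0.10. With c = 0.4 they are 0.64 and 0.46. Approximate power at 20 per arm is 60% for c = 0 and 34%, 20% and 13% for c = 0.2, 0.4 and 0.6. This is an outer case: it counts every subject in c as an event. Setting those subjects apart would not restore the full 60%, because fewer would remain at risk.

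**The case against.** Several objections are sound and limit the point.

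- A reader might infer that no baseline infection status exists. The documents say otherwise: the ulcer stage, laboratory values and anti-infective drugs are taken at baseline, with tissue for bacterial load where it is collected. The gap is in the use of these data.
- A reader might infer that residual infection biases the result against one product. Both arms receive Stravix over NPWT and allocation is random, so neither arm is systematically disadvantaged.
- A reader might infer that every subject enters infected. The Section 14 wording is an aside explaining why planned procedures are not adverse events. It is not an eligibility rule, and Section 4 lists routes of recruitment without mentioning infection.
- The endpoint may mean bacterial load, not the clinical grade, since that is how Section 7 uses the phrase. A like-for-like baseline would then exist wherever tissue is taken, but no baseline term is planned for it either. Mixing entry with later infection is left open by an undefined endpoint; the plan does not prescribe it.
- The simulations use four grades where the plan has five, and a rank test where it names chi-square. The 0.8 SD shift and the correlations are not from the documents. Unadjusted power should not vary with the correlation, so its spread of 61 to 64% is simulation noise, about as large as the gain at correlation 0.4.
- It is tempting to count an infection as new only if it was absent at baseline or is of higher grade. That would miss a subject who recovers and is later infected at the same or a lower grade. Section 4 foresees recovery from infection during the study, so the documents do not support such a rule.

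What remains is that the plan records entry infection, may well admit many infected subjects, and compares the arms without using it.

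**Conclusion.** The point holds as a weakness of endpoint definition and analysis. The infection comparison ignores information recorded before treatment, and the clinical grade has no visit at which it must be assigned. At 20 per arm, the chance of an entry imbalance of at least 20 points is 23 to 27% if 30 to 70% enter infected. The consequences are lost power and an uncorrected imbalance in the trials where one occurs; the overall error rate stays near 5% and there is no systematic bias.

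The gain from adjusting is conditional. It is about 3 points of power in the grade simulation at a correlation of 0.4 and 12 to 17 points at 0.6 to 0.7, for an assumed 0.8 SD shift. This is a secondary endpoint of a self-described pilot, so the point is moderate, but the remedy is cheap and a grade not recorded before placement cannot be reliably recovered later.

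**What to change.** 1. **Define the endpoint.** State whether it is the 1 to 5 grade of Section 4 (Infection Evaluation) or bacterial load, and at which visit it is analysed. If bacterial load is chosen, allow for the footnote that limits tissue collection to surgical debridement.
2. **Record the same measure at baseline, before Stravix is placed**, and add it to the Schedule of Events there and at the analysed visit.
3. **Use it in the comparison.** Compare arms adjusted for the baseline value or stratified by it, for example by rank ANCOVA or a stratified Wilcoxon test. If the baseline grade is missing, stratify by the ulcer's infection stage (A or C v B or D).
4. **Report separately** infections present at entry and those arising after placement, without a rule that a later infection counts only if it was absent at baseline or is of higher grade.
5. **Reconcile the text.** Sections 3, 4 and 14 differ in how they describe infection at entry. What Section 14 means by a new infection should be reconciled with the early-termination text in Section 3 and the infection-related sampling in Section 4.

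The cost is one case report form field and one covariate in Section 7. Two practical limits apply: temperature is not named among the baseline vital signs although the infection evaluation relies on it, and grade 5 needs a bone diagnosis that examination and white cell count do not supply.
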